4.2 Handling of missing data and drop-outs

The data will be planned and analysed using the intent-to-treat principle (ITT). If missing data is >5%, the possibility of multiple imputation will be examined. We intend to minimise missing data and will for example design mandatory questions in the questionnaires and send reminders to participants to complete the follow-up questionnaires.

The dropout rate is estimated at about 10 % and was taken into account accordingly in the sample size calculation. Recruitment has to take place during pregnancy in order to be able to observe the evaluation of the intervention. In obstetrics, it is never possible to predict how the birth will proceed and how the childbirth experience will affect the participants. Therefore, loss of follow-up for medical reasons cannot be avoided. The research assistants as well as the lead midwife will monitor the study process on site and remind the participants to fill in the questionnaires.

5 REGULATORY ASPECTS AND SAFETY

5.1 Local regulations / Declaration of Helsinki

This study is conducted in compliance with the protocol, the current version of the Declaration of Helsinki, the ICH-GCP the HRA as well as other locally relevant legal and regulatory requirements.

5.2 (Serious) Adverse Events and notification of safety and protective measures

An Adverse Event (AE) is any untoward medical occurrence in a patient or a clinical investigation subject which does not necessarily have a causal relationship with the trial procedure. An AE can therefore be any unfavourable or unintended finding, symptom, or disease temporally associated with a trial procedure, whether or not related to it.

A Serious Adverse Event (SAE) (ClinO, Art. 63) is any untoward medical occurrence that

- Results in death or is life-threatening,
- Requires in-patient hospitalisation or prolongation of existing hospitalisation,
- Results in persistent or significant disability or incapacity, or
- Causes a congenital anomaly or birth defect

Both Investigator and Sponsor-Investigator make a causality assessment of the event to the trial intervention, (see table below based on the terms given in ICH E2A guidelines). Any event assessed as possibly, probably or definitely related is classified as related to the trial intervention.

Relationship	Description
Definitely	Temporal relationship Improvement after dechallenge* Recurrence after rechallenge (or other proof of drug cause)
Probably	Temporal relationship Improvement after dechallenge No other cause evident
Possibly	Temporal relationship Other cause possible
Unlikely	Any assessable reaction that does not fulfil the above conditions
Not related	Causal relationship can be ruled out

*Improvement after dechallenge only taken into consideration, if applicable to reaction

Both Investigator and Sponsor-Investigator make a severity assessment of the event as mild, moderate or severe. Mild means the complication is tolerable, moderate means it interferes with daily activities and severe means it renders daily activities impossible.

Reporting of SAEs (see ClinO, Art. 63)

All SAEs are documented and reported immediately (within a maximum of 24 hours) to the Sponsor-Investigator of the study.

If it cannot be excluded that the SAE occurring in Switzerland is attributable to the intervention under investigation, the Investigator reports it to the Ethics Committee via BASEC within 15 days.

Follow up of (Serious) Adverse Events

Participants, who experience an (Serious) Adverse Event during childbirth will be contacted after terminating the study to answer questions, to ensure . If necessary, contact details of professionals, who could offer additional support, will be provided.

Notification of safety and protective measures (see ClinO, Art 62, b)

If immediate safety and protective measures have to be taken during the conduct of the study, the investigator notifies the Ethics committee of these measures, and of the circumstances necessitating them, within 7 days.

5.3 (Periodic) safety reporting

An annual safety report (ASR) is submitted once a year to the local Ethics Committee by the Investigator (ClinO, Art. 43 Abs 1).

5.4 Radiation

Not applicable

5.5 Pregnancy

All participants will be pregnant because of the nature of the study. Reporting of pregnancies will therefore not be necessary.

5.6 Amendments

Substantial changes to the study setup and study organization, the protocol and relevant study documents are submitted to the Ethics Committee for approval before implementation. Under emergency circumstances, deviations from the protocol to protect the rights, safety and well-being of human subjects may proceed without prior approval of the Ethics Committee. Such deviations shall be documented and reported to the Ethics Committee as soon as possible.

Substantial amendments are changes that affect the safety, health, rights and obligations of participants, changes in the protocol that affect study objective(s) or central research topic, changes of study site(s) or of study leader and sponsor (ClinO, Art. 29).

A list of substantial changes is also available on www.swissethics.ch.

A list of all non-substantial amendments will be submitted once a year to the competent EC together with the ASR.

5.7 Notification and reporting upon completion, discontinuation or interruption of the study

The Sponsor-Investigator may terminate the study prematurely according to certain circumstances, e.g.

- Ethical concerns,
- Insufficient participant recruitment,
- When the safety of the participants is doubtful or at risk (e.g. when the benefit-risk assessment is no longer positive),
- Alterations in accepted clinical practice that make the continuation of the study unwise, or
- Early evidence of harm or benefit of the experimental intervention

Upon regular study completion, the Ethics Committee is notified via BASEC within 90 days (ClinO, Art. 38).

Upon premature study termination or study interruption, the Ethics Committee is notified via BASEC within 15 days (ClinO, Art. 38).

A final report is submitted to the Ethics Committee via BASEC within a year after completion or discontinuation of the study, unless a longer period is specified in the protocol (ClinO, Art. 38).

5.8 Insurance

In the event of study-related damage or injuries, the liability of Zurich University of Applied Sciences provides compensation, except for claims that arise from misconduct or gross negligence. ZHAW has a liability insurance with an overall sum insured over CHF ten Mio. With one Mio. per participants to cover personal injuries. The study is registered correctly with Zurich Insurance.

6 FURTHER ASPECTS

6.1 Overall ethical considerations

Health-related data is considered to be sensitive personal data by the Federal Act on Data Protection. Thus, procedures must comply with the current GCP standards and the Human Research Act of Switzerland. Throughout the research process, we will pay close attention to dynamic ethical issues. We consider general ethical issues when designing, implementing, and reporting our research (e.g., following publication rules).

In the study information and the consent form, the study and its purpose will be described, and it will be highlighted that participation is entirely voluntary and that participation can be refused or withdraw at any stage, with no further consequences. Furthermore, participants will be informed about the intended research project and all benefits and risks (principle of autonomy). All data will be encoded which makes it impossible to conclude on a specific data without the participant identification list. The participant identification list will only be accessible to a sub-group of the study personnel and only people with appropriate training in Good Clinical Practice (GCP). Data will be treated confidentially. We conclude that our research is in the interest of the childbearing women (principle of fairness or justice), and that the women could directly benefit from the antenatal education class and therefore from the research (principle of beneficence). In order to minimize outside influence and manipulation, we openly account for our purposes and methods.

We will validate an antenatal education class including a breathing and relaxation technique. The planned study consists of the validation and evaluation of an antenatal education class to increase women's self-confidence as well as their self-efficacy. The entire project of development, evaluation and implementation is thought through and elaborated with the help of the MRC Framework (Michie et al., 2008, 2011).

Finally, we will seek ethical approval for the evaluation of the antenatal education class including a breathing and relaxation technique to increase women's self-efficacy at the Ethics Committee of the Canton Zurich.

6.2 Risk-benefit assessment

We do not expect any serious risks for the participants. Antenatal education is part of antenatal care and is financed by the obligatory health insurance (OKP). Every woman has the opportunity to attend an antenatal education class if she would like to. Women benefit from the information provided in the antenatal class as well as the exercises to support them during the labour and birth. However, participants will complete questionnaires during pregnancy and after birth. This could be an additional challenge and a larger workload for women. In addition, it is possible that the childbirth experience will become present through the questionnaires. This is why the participants are offered the opportunity to get in touch with the supervising midwife and to have a follow-up talk with the birth attendant midwife. If further support is indicated, it is possible to involve the relevant specialists at the Cantonal Hospital Winterthur.

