3.3 Study procedures

The study duration will be one and a half year. The recruitment period will be one year. Participants will be recruited in their second or beginning of third trimester of pregnancy. After

signing the consent form, participants will register for an antenatal education class. Due to the course organisation at the Cantonal Hospital Winterthur, randomisation is conducted at the course level. The randomisation is performed by envelopes with the corresponding information about the course (intervention yes or no). In the randomisation process the sponsor-investigator and local project leader will be excluded.

Prior to the start of the classes, the participants fill in the online baseline questionnaire, which was sent to them by email. After the antenatal class, at around 36 weeks of gestation, the participants complete the education online questionnaire. The study assistant transfers the birth data anonymously directly from the clinic system to REDCap®. Finally, the postpartum online questionnaire is completed within four weeks after the birth (see Figure 1).

[figure not shown]

Figure 5 Study process

The following table provides an overview on the study instruments and the timing of their application for data collection:

Table 1 Study instruments and timing of application

Questionnaires / Interview	Time of application	Content	Filled in by
Baseline questionnaire (T0)	After recruitment before the antenatal education class started	Socio-demographic data, medical and obstetric history, German versions of the Childbirth-Self-Efficacy Inventory	Participant
Education questionnaire (T1)	After intervention (around 36 weeks of gestation)	Data about the antenatal education class, German versions of the Childbirth-Self-Efficacy Inventory	Participant
Labour and birth questionnaire (T2)	After birth	Labour and birth outcomes for mother and child, early postpartum period	Research assistant
Postnatal questionnaire (T3)	Early postnatal questionnaire (within 4 weeks after birth)	German version of the Childbirth experience questionnaire, postnatal quality of life, Data about the antenatal education class	Participant
Semi-structured interview guide	After birth (within 10 working days)	Women's experience during birth, feasibility of the breathing and relaxation technique learned, self-efficacy and self-confidence observed	Research assistant and birth attendant midwives

3.3.1 Potential bias and measures, to reduce them:

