Appendix 1: Schedule of assessments

Time (hour, day, week)	>-1 day	> 12 weeks of gestation	2nd trimester	After intervention (~36 weeks gestation)	Birth records	Postnatal (4 to 8 weeks after birth)
Visit/Activity	Information (visit or telephone)	Screening (face-to-face or mail post)	Baseline online survey	Intervention online survey	Maternal and neonatal birth data	Postnatal online survey
Oral and written patient information	+					
Written consent		+				
Inclusion-/exclusion criteria	+	+				
Medical history			+		+	
Physical examination						
Participant characteristics			+		+	
Intervention					+	
Questionnaire			+		+	+
Sampling						
Safety		+			+

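### The protocol names a harm from its own questionnaires but does not actively look for it, nor for adverse events between class and birth or after the early postpartum period

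*Combined protocol and SAP*

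**What the plan says.** Section 6.2 expects no serious risk but names one psychological one: "In addition, it is possible that the childbirth experience will become present through the questionnaires". Its response follows directly: "This is why the participants are offered the opportunity to get in touch with the supervising midwife and to have a follow-up talk". It adds: "If further support is indicated, it is possible to involve the relevant specialists at the Cantonal Hospital Winterthur".

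The instrument table in section 3.3 gives the content of T3 as "German version of the Childbirth experience questionnaire, postnatal quality of life, Data about the antenatal education class". T1, at about 36 weeks, holds data on the class and the self-efficacy inventory. The participant completes both. The birth form (T2), completed by the research assistant, covers labour, birth and the early postpartum period.

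Section 5.2 defines adverse events broadly: "An AE can therefore be any unfavourable or unintended finding, symptom, or disease temporally associated with a trial procedure, whether or not related to it". For serious events it says: "All SAEs are documented and reported immediately (within a maximum of 24 hours) to the Sponsor-Investigator of the study". Its follow-up paragraph refers to women whose event occurred during childbirth.

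Appendix 1 has a Safety row with two marks. Its last two columns are headed "Maternal and neonatal birth data" and "Postnatal online survey".

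**The concern.** The protocol has a duty to report harms but describes no active way of finding them outside the birth record. That includes the one psychological harm it names itself. A woman distressed by T3 is recorded only if she comes forward. The same holds for a health problem during home practice, which only the intervention arm is given (section 2.4.2).

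Two things are at stake. First, a report of no questionnaire-related distress could not be interpreted, because nobody asked, and analysts cannot recover the information afterwards. Second, the annual safety report (section 5.3) and the option to stop for doubtful participant safety (section 5.7) would draw on birth data plus whatever is volunteered. Volunteered reports are a weak basis for comparing arms when the class midwives know the allocation (section 3.3.1).

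**Working it through.** The plan gives no figure to reproduce, so the check sets the passages side by side.

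1. **Where the named harm falls.** Section 6.2 does not tie the risk to one survey. T3 carries the childbirth experience questionnaire and is the only participant survey after the study birth, so the risk lies mainly there. It does not lie only there. Section 3.1 does not exclude women who have given birth before, and the baseline survey (T0) takes an obstetric history, so an earlier birth could resurface during pregnancy.

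2. **What each contact after the start of the class is listed to collect (section 3.3).**
   - T1, about 36 weeks, participant: class data and self-efficacy. No adverse-event, admission or distress item.
   - T2, after birth, research assistant: labour and birth outcomes and the early postpartum period.
   - T3, participant: childbirth experience, quality of life and class data. No adverse-event, admission or distress item.

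   Neither of the two participant surveys after the class lists a safety item. With 70 women planned (section 4.1), that is 70 × 2 = 140 planned survey completions without a safety question.

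3. **Other routes to staff.**
   - The 24-hour rule in section 5.2 covers every serious event. It gives no collection period, no method and no person charged with asking.
   - The section 5.2 follow-up names only events during childbirth.
   - The staff reminders in section 4.2 concern completing the questionnaires.
   - The midwife workshop in section 7.1 covers the course concept and the technique.
   - Monitoring in section 8 checks 10% of labour and birth data.
   - No section assigns anyone to read survey answers for safety.

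4. **What Appendix 1 adds.** The table has a label plus six time columns, so seven cells. In the available text the Safety row has six cells, so one is missing. If that is the only defect, the two marks fall as follows:
   - cell lost at the end: screening and birth records;
   - cell lost between the marks: screening and postnatal survey;
   - cell lost before the first mark: baseline and postnatal survey.

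   As it stands (the first case), the row has no mark at about 36 weeks and none postnatally. Under the other two, the postnatal survey is marked. Two further rows conflict with section 3.3. The Intervention row has its only mark under birth data, although the class comes before T1. The Questionnaire row has no mark at about 36 weeks, although T1 is planned then. The column positions therefore cannot carry the point. Steps 1 to 3 do not depend on them.

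5. **End of any collection window.** Section 3.3 places T3 within 4 weeks after birth, and Appendix 1 places it at 4 to 8 weeks. The latest dates differ by 8 − 4 = 4 weeks.

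**The case against.** The strongest reply is that this is a risk category A study (section 3.2) of classes that are already part of antenatal care, with broad safety rules in place. Section 5.2 makes all serious events reportable at any time and limits neither serious nor other events to particular visits. Section 6.2 offers a midwife contact, a talk and specialist referral for exactly this harm. T2 reaches into the early postpartum period and T3 measures quality of life. More items add to the questionnaire burden that section 6.2 already acknowledges.

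Much of this stands, and it limits the point. A reader might infer that safety is collected only at screening and from birth records, so that the named harm and every event between class and birth go unseen. The documents do not support that. It reads one row of an unreliable table as fact, and under another placement of the missing cell that row marks the postnatal survey. It also overlooks the unrestricted reporting rule and the postpartum content of T2. Nor do the documents give a length for the antenatal interval. An assumed class start at 20 to 28 weeks and birth at 40 weeks would give 40 − 28 = 12 to 40 − 20 = 20 weeks, but only as a worst case in which no carer hears of anything.

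The reply does not supply a means of detection. A reporting rule applies once staff know of an event. The section 6.2 offer is support on the woman's initiative, not recording. Quality of life is an outcome with no threshold or alert attached.

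**Conclusion.** The point holds in a limited form. The named harm, and adverse events between class and birth or after the early postpartum period, are not actively sought and depend on volunteered reports. This concerns how events are found; the duty to report them is in place. It applies to up to 70 women and to both participant surveys after the class.

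The conclusion assumes that the section 3.3 table lists the survey content in full, and that no procedure outside the protocol has staff ask about health between contacts. If the printed Appendix 1 does mark Safety at T1 or T3, section 3.3 still lists no item to deliver it, and the two must be reconciled. In a low-risk trial this does not undermine the design or the primary analysis. It should still be corrected before the surveys are used, because the information cannot be recovered later.

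**What to change.** - **T3:** add a short item asking whether the survey, or recalling the birth, was distressing and whether the woman would like to be contacted.
- **T1 and T3:** add one item on health problems or unplanned admissions since the last survey, expressly excluding the admission for the birth. Without that exclusion almost every woman would answer yes at T3, since all plan to give birth in hospital.
- **Alert:** have REDCap send a positive answer to authorised staff who hold the identification list, to start the assessment in section 5.2 and the support offer in section 6.2. Section 3.2 calls the survey anonymised, while section 7.3 describes coded data with a separate list. State that the alert carries the study number only and that these staff re-identify the woman.
- **Reporting:** state the period and method of adverse-event collection in section 5.2, and tabulate the answers by arm.
- **Appendix 1:** mark Safety at T1 and T3, and reconcile the table with section 3.3, including the Intervention and Questionnaire rows and the timing of T3.

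The cost is slightly longer surveys, one automatic alert, a protocol wording change, and some re-identification and triage by existing staff. No visit is added.

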7 QUALITY CONTROL AND DATA PROTECTION

7.1 Quality measures

Several quality measures will be installed:

- The antenatal midwives in the Canton Hospital Winterthur will be trained before the intervention. The investigator organises a 2-hour workshop where the course concept as well as the breathing and relaxation technique is discussed and practised together. In addition, the investigator is always available to answer questions from the midwives. Midwives receive a handout with the background and the breathing and relaxation technique.
- Data will be collected using REDCap®. REDCap® is a secure web application for building and managing surveys as well as databases compliant to the demands of GCP Swiss regulations regarding clinical studies. An audit trail will document all changes made to the data. The audit trail contains the person that made the changes, the time the change was made, and the data before the change. Automated checks implemented in the data entry field further check the data for plausibility and completeness as it is saved. The software gives continuous feedback to the users as

how to correct the data in order to comply to defined rules. Erroneous and missing data are marked for follow up.

- The investigator at ZHAW will be responsible for data checking and data storing using REDCap® correctly.

For quality assurance the sponsor, the Ethics Committee or an independent trial monitor may visit the research sites. Direct access to the source data and all study related files is granted on such occasions. All involved parties keep the participant data strictly confidential.

7.2 Data recording and source data

Quantitative data (questionnaire data, labour and birth data from medical records) will be entered by a midwife and a research assistant in the study site to the open source software REDCap® (Research Electronic Data Capture). REDCap® is an international commercial study software compliant to the demands of the current GCP standards and the Human Research Act of Switzerland (<https://www.project-redcap.org/software/>). REDCap® is a secure web application for building and managing surveys as well as databases compliant to the demands of GCP Swiss regulations regarding clinical studies. Data can be entered from any computer connected to the internet providing current browser software (e.g., Mozilla Firefox). Data entry fields in REDCap® are in a specific format that allows only entering data in this format (e.g., date fields, number fields). An audit trail will document all changes made to the data. The audit trail contains the person that made the changes, the time the change was made, and the data before the change. Automated checks implemented in the data entry field further check the data for plausibility and completeness as it is saved. The software gives continuous feedback to the users as how to correct the data in order to comply to defined rules. Erroneous and missing data are marked for follow up. The database will contain a CRF for each participant with a unique study ID and the year of birth. It will not contain any further personal data such as name or birth date.

We plan to provide a protocol with detailed descriptions on how the data was recorded. The metadata will include details about the date and time of data collection, data processing methods, analytical steps, units of measurements, and identifier on the person performing processing steps. This information will be stored in a README-file for each dataset.

